**Table 13****Clinical Procedures: Exploratory Biomarkers**

Procedure	Description
Biomarker samples	Blood samples will be collected for exploratory biomarker assessments (serum and DNA and RNA analyses)

## 8.2 Blood Samples

During the study, blood will be taken from each subject for laboratory safety assessments, PK evaluations, ANA, MSA and MAA, exploratory biomarkers, and virology (HBV, HCV, and HIV) samples. Approximately 360.5 mL of blood will be drawn from each subject during Study Period 1 and Study Period 2. An additional 8 mL of blood per year of study participation will be collected during Study Period 3, with an additional 7.5 mL collected for virology retention at the EOP3 Visit, leading to a maximum of 392 mL collected over all 3 study periods. Detailed information on the volume of blood to be sampled for each assessment will be available in the ICF and laboratory manual.

Repeat or unscheduled blood samples may be taken for safety reasons or for technical issues with the samples and will be in addition to the estimated 392 mL blood volume for scheduled assessments.

Refer to the study manual for details about the collection, storage, handling and processing of blood samples.

## 8.3 Retention of Samples

Retention samples of serum for virology will be obtained as specified in the [Schedule of Assessments](#). Virology retention samples will be stored at the central laboratory. In case of any evidence for a possible treatment-emergent virus infection within 1 year after study completion, the retention sample will be analyzed in the central laboratory.

All exploratory biomarker samples collected during the study will be retained and destroyed within 10 years after completion of the study. Biomarker retention samples will be stored at CSLB ([name]). Refer to the study manual for further details about the storage and destruction of retention samples.

## 8.4 Prior and Concomitant Therapies

All medications taken by a subject within 3 months before Baseline are considered prior therapy and must be documented in the eCRF.

Previous medications and therapies for DM that the subject has received within 1 year before Baseline must be documented in the eCRF. If possible, all available data regarding the subject's treatment with IgG therapy since being diagnosed with DM should be recorded in the subject's eCRF.

All drugs and/or procedures currently being administered to a subject at the time of signing informed consent, and which continue to be taken in addition to IgPro20 or placebo during the study, as well as drugs and/or procedures initiated after the first infusion of study product, are regarded as concomitant therapies and must be documented as such in the eCRF.

Any prohibited dose adjustments in permitted concomitant therapies (see [Section 7.2](#)) will lead to withdrawal from treatment.

## 8.5 Visit Schedule

### 8.5.1 Assessment Time Windows

The timing and frequency of the study visits are described in the [Schedule of Assessments](#).

Time windows for all assessments are detailed in Table 14.

**Table 14** **Time Windows for Assessments**

Visit/Procedure	Time window (relative to scheduled visit/procedure)
Screening	Up to 2 months before Baseline
Week 2 and all subsequent study visits in Study Period 1 and Study Period 2	$\pm$ 3 days
Monthly study visits in Study Period 3	$\pm$ 7 days
Physical examination, to include Physician Global Damage Assessment only at Screening	Before first SC infusion on Week 1 A
Vital signs, including body weight	Before first SC infusion on Week 1 and Week 2 A
Urine collection for pregnancy test B	Before first SC infusion on Week 1 A
Blood collection for laboratory tests	Before first SC infusion on Week 1 and Week 2 A
Blood collection for rich PK (serum IgG and exploratory biomarkers)	Week 37, trough sample collection at study visit Week 37, $24 \pm 3$ h relative to the start of first infusion Week 37, $48 \pm 3$ h relative to the start of first infusion Week 37, $72 \pm 3$ h relative to the start of first infusion Week 37, $120 \pm 3$ h relative to the start of first infusion Week 37, $168 \pm 3$ h relative to the start of first infusion
Subject SC Infusion Diary review	At the end of SC infusions on Week 1 and Week 2 A
Adverse event documentation	Before first SC infusion on Week 1 and Week 2 A
Safety assessment documentation	Before first SC infusion on Week 1 and Week 2 A

Visit/Procedure	Time window (relative to scheduled visit/procedure)
Concomitant therapy documentation	Before first SC infusion on Week 1 and Week 2 A
Physiotherapy documentation	Before first SC infusion on Week 1 and Week 2 A
Efficacy assessments	Before first SC infusion on Week 1 and Week 2 A

h = hour; IgG = immunoglobulin G; PK = pharmacokinetic; SC = subcutaneous.

A For all other study visits, SC infusions are not performed at the study visit.

B Urine pregnancy test is to be completed for all females of reproductive potential.

## 8.5.2 Screening

All subjects must provide written informed consent before any study-specific assessments or procedures are performed (see [Section 12.3](#)).

The Screening examination must be performed no more than 2 months before the intended Baseline date. Note: A duration of 2 months may be required from last IgG dose to Baseline for subjects on IgG therapy before Screening (see [Section 7.3](#)). For subjects enrolling without active DM rash, the other objective evidence to confirm disease activity must be reviewed by CSLB medical monitoring staff (or delegate) before final eligibility is determined and the subject is randomized. The other objective evidence to confirm disease activity may include any of the following: MRI scan, electromyogram, muscle biopsy, or CK > 4 × ULN within 3 months before Baseline. If a potential subject fails eligibility for a reason other than DM diagnosis or disease activity, the potential subject may be rescreened 1 time for the study and all Screening assessments must be repeated.

The following procedures will be conducted and documented at the Screening Visit as specified in the Schedule of Assessments for Screening ([Table 1](#)):

- Obtain written informed consent and register the subject via IRT
- Relevant medical and surgical history to include DM history details (including age at first diagnosis) from time of diagnosis (available surgical history for the past 5 years), and prior treatments for DM
  - Available DM treatment history (eg, corticosteroids, other immunosuppressants, antimalarials, IgG [to include IgG details including type of therapy {eg, IV or SC}, method of administration {eg, central venous port, peripherally inserted central catheter}, dosage and frequency, and types of AEs experienced associated with the method of administration, since diagnosis}])

- Documentation of previous age-appropriate cancer screening
- Demographics
- Review of inclusion and exclusion criteria including the EULAR/ACR classification criteria for DM
- CDASI
- General physical exam, including height
- 12-lead electrocardiogram (ECG)
- Body weight
- Vital signs
- Wells' Criteria
- Collection of blood sample for serum hCG pregnancy test, if applicable
- Collection of blood samples to assess the following:
  - Serum IgG level
  - Hematology
  - ABO blood group (blood group type A, type B, type AB, or type O) and Rhesus (Rh) factor
  - Muscle enzymes
  - Other biochemistry
  - Thrombophilic abnormality screen
  - Coagulation
  - ANA, MSA, and MAA
  - Virology
- Document AEs
- Document concomitant therapies
- Document physiotherapy
- Individual CSMs
- Physician Global Damage Assessment

---

If the subject is not eligible for the study, the primary reason for screen failure must be entered in the IRT.

### 8.5.3 Study Period 1

Study Period 1 is a 24-week, double-blind, placebo-controlled treatment period during which participating subjects receive either IgPro20 or placebo at 0.5 g/kg SC on a weekly basis.

Study Period 1 starts with Baseline/Week 1 and continues through the Week 25 Visit (24 weeks  $\pm$  3 days after the first SC infusion of IMP). Study assessments will be performed as specified in the Schedule of Assessments for Study Period 1 ([Table 2](#)).

#### 8.5.3.1 Baseline/Week 1

The Baseline and Week 1 visits occur at the same study visit; however, all Baseline procedures must be completed before the Week 1 procedures begin. The final eligibility criterion to be met is no clinically relevant improvement between Screening and Baseline ([Section 4.1.2](#), Exclusion criterion 4). This determination will be made based on the Treating and Evaluating Physicians' clinical judgement following review of the efficacy assessments performed at Screening and Baseline.

Subjects who complete all Screening and Baseline CSM assessments and who fulfill all eligibility criteria (ie, eligible subjects) will be randomized. At the Baseline Visit, the following procedures are to be conducted and documented:

##### **Baseline**

- Confirm eligibility
- Randomization into double-blind treatment (see [Section 6.2](#))
- General physical examination
- Body weight
- Waist circumference
- IMP assignment
- Vital signs
- Safety assessments
- Collection of urine sample for hCG pregnancy test, if applicable

- Collection of blood samples for virology retention and exploratory biomarkers (serum and DNA/RNA analyses)
- Collection of blood samples to assess the following:
  - Hematology
  - Glycated hemoglobin (HbA1c)
  - Muscle enzymes
  - Hemolysis
  - Other biochemistry
  - Coagulation
  - Serum IgG
- Document AEs
- Document concomitant therapies
- Document any change to physiotherapy since the previous study visit
- Assess for clinically relevant improvement
- Individual CSMs
- CDASI
- 5-D Itch Score
- Timed Up and Go
- EQ-5D-5L, WPAI-GH

### **Week 1**

- Document AEs
- Document concomitant therapies
- Training and supervision of first IMP SC infusion
- Supervision of subject SC Infusion Diary entry

### 8.5.3.2 Week 2

The following procedures will be conducted at 1 week  $\pm$  3 days after the first SC infusion of IMP:

- Body weight
- IMP assignment
- Vital signs
- Safety assessments
- Collection of blood samples to assess the following:
  - Hematology with peripheral blood smear
  - Hemolysis
  - Coagulation
  - Serum IgG
- Training and supervision of IMP SC infusion for Week 2
- Supervision of subject SC Infusion Diary entry
- Document AEs
- Document concomitant therapies
- Document any change to physiotherapy since the previous study visit

Starting with Week 3, the subject will adjust their first dosing day so that no SC infusions occur on the day of a study visit. Site instruction for this transition should be provided.

### 8.5.3.3 Week 5

The following procedures will be conducted at 4 weeks  $\pm$  3 days after the first SC infusion of IMP:

- Body weight
- IMP assignment
- Vital signs
- Safety assessments
- Collection of urine sample for hCG pregnancy test, if applicable

- Collection of blood samples for exploratory biomarkers (serum and RNA analyses)
- Collection of blood samples to assess the following:
  - Hematology with peripheral blood smear
  - Muscle enzymes
  - Hemolysis
  - Coagulation
  - Serum IgG
- Subject SC Infusion Diary review
- Document AEs
- Document concomitant therapies
- Document any change to physiotherapy since the previous study visit
- DOW assessment
- Individual CSMs
- CDASI

#### 8.5.3.4 Week 9

The following procedures will be conducted at 8 weeks  $\pm$  3 days after the first SC infusion of IMP:

- Body weight
- IMP assignment
- Vital signs
- Safety assessments
- Collection of urine sample for hCG pregnancy test, if applicable
- Collection of blood samples for exploratory biomarkers (serum analysis)
- Collection of blood samples to assess the following:
  - Hematology
  - Muscle enzymes
  - Other biochemistry

- Coagulation
- Serum IgG
- Subject SC Infusion Diary review
- Document AEs
- Document concomitant therapies
- Document any change to physiotherapy since the previous study visit
- DOW assessment
- Individual CSMs
- CDASI
- 5-D Itch Score
- Timed Up and Go

### 8.5.3.5 Week 13

The following procedures will be conducted at 12 weeks  $\pm$  3 days after the first infusion of IMP:

- Body weight
- IMP assignment
- Vital signs
- Safety assessments
- Collection of urine sample for hCG pregnancy test, if applicable
- Collection of blood samples to assess the following:
  - Muscle enzymes
  - Coagulation
- Subject SC Infusion Diary review
- Document AEs
- Document concomitant therapies
- Document any change to physiotherapy since the previous study visit
- DOW assessment

- Individual CSMs
- CDASI
- EQ-5D-5L, WPAI-GH, TSQM-9

### 8.5.3.6 Week 17

The following procedures will be conducted at 16 weeks  $\pm$  3 days after the first SC infusion of IMP:

- Body weight
- IMP assignment
- Vital signs
- Safety assessments
- Collection of urine sample for hCG pregnancy test, if applicable
- Collection of blood samples for exploratory biomarkers (serum analysis)
- Collection of blood samples to assess the following:
  - Hematology
  - Muscle enzymes
  - Other biochemistry
  - Coagulation
  - Serum IgG
- Subject SC Infusion Diary review
- Document AEs
- Document concomitant therapies
- Assess if subject has clinically relevant improvement, and if so, subjects must initiate oral corticosteroid taper (see [Section 5.3.2](#))
- Document any change to physiotherapy since the previous study visit
- DOW assessment
- Individual CSMs
- CDASI

- 5-D Itch Score
- Timed Up and Go

### 8.5.3.7 Week 21

The following procedures will be conducted at 20 weeks  $\pm$  3 days after the first SC infusion of IMP:

- Body weight
- IMP assignment
- Vital signs
- Safety assessments
- Collection of urine sample for hCG pregnancy test, if applicable
- Collection of blood samples for exploratory biomarkers (serum analysis)
- Collection of blood samples to assess the following:
  - Muscle enzymes
  - Coagulation
  - Serum IgG
- Subject SC Infusion Diary review
- Document AEs
- Document concomitant therapies
- Document any change to physiotherapy since the previous study visit
- DOW assessment
- Assess if subject has clinically relevant improvement, and if so, subjects must initiate oral corticosteroid taper (see [Section 5.3.2](#))
- Individual CSMs
- CDASI

### 8.5.3.8 Week 25

The following procedures will be conducted at 24 weeks  $\pm$  3 days after the first SC infusion of IMP:

- General physical examination
- Body weight
- Waist circumference
- IMP assignment
- Vital signs
- Safety assessments
- Collection of urine sample for hCG pregnancy test, if applicable
- Collection of blood samples for exploratory biomarkers (RNA and serum analyses)
- Collection of blood samples to assess the following:
  - Hematology
  - HbA1c
  - Muscle enzymes
  - Other biochemistry
  - Coagulation
  - Serum IgG
  - ANA, MSA, and MAA
- Subject SC Infusion Diary review
- Document AEs
- Document concomitant therapies
- Document any change to physiotherapy since the previous study visit
- DOW assessment
- Assess if subject has clinically relevant improvement, and if so, subjects must initiate oral corticosteroid taper (see [Section 5.3.2](#))
- Individual CSMs

- CDASI
- 5-D Itch Score
- Timed Up and Go
- EQ-5D-5L, WPAI-GH, TSQM-9

### 8.5.4 Study Period 2

During Study Period 2, all participating subjects will receive 28 weeks of active treatment with IgPro20 at 0.5 g/kg SC on a weekly basis. Study Period 2 starts with administration of IgPro20 at Week 25, after all Week 25 assessments (as specified in [Section 8.5.3.8](#)) have been completed. Study Period 2 continues through the Week 53 Visit when the subject's eligibility for continuation of IgPro20 treatment in Study Period 3 will be confirmed ([Section 8.5.4.7](#)). Subjects not eligible for participation in Study Period 3 must complete the Week 56 Safety Follow-up Telephone Call ([Section 8.5.4.8](#)).

Study assessments will be performed as specified in the Schedule of Assessments for Study Period 2 ([Table 2](#)).

#### 8.5.4.1 Week 29

The following procedures will be conducted at 28 weeks  $\pm$  3 days after the first SC infusion of IMP:

- Body weight
- IMP assignment
- Vital signs
- Safety assessments
- Collection of urine sample for hCG pregnancy test, if applicable
- Collection of blood samples to assess the following:
  - Muscle enzymes
  - Coagulation
- Subject SC Infusion Diary review
- Document AEs
- Document concomitant therapies

- Document any change to physiotherapy since the previous study visit
- Assess if subject has clinically relevant improvement, and if so, initiate oral corticosteroid taper
- Individual CSMs
- CDASI

#### 8.5.4.2 Week 33

The following procedures will be conducted at 32 weeks  $\pm$  3 days after the first SC infusion of IMP:

- Body weight
- IMP assignment
- Vital signs
- Safety assessments
- Collection of urine sample for hCG pregnancy test, if applicable
- Collection of blood samples to assess the following:
  - Hematology
  - Muscle enzymes
  - Other biochemistry
  - Coagulation
- Subject SC Infusion Diary review
- Document AEs
- Document concomitant therapies
- Document any change to physiotherapy since the previous study visit
- Assess if subject has clinically relevant improvement, and if so, initiate oral corticosteroid taper
- Individual CSMs
- CDASI
- 5-D Itch Score

- Timed Up and Go
- EQ-5D-5L, WPAI-GH, TSQM-9

### 8.5.4.3 Week 37

The following procedures will be conducted at 36 weeks  $\pm$  3 days after the first SC infusion of IMP:

- Body weight
- IMP assignment
- Vital signs
- Safety assessments
- Collection of urine sample for hCG pregnancy test, if applicable
- Collection of blood samples for exploratory biomarkers (serum analysis)
- Collection of blood samples to assess the following:
  - Muscle enzymes
  - Coagulation
  - Serum IgG
- Additional sampling for rich PK analysis, if applicable
- Subject SC Infusion Diary review
- Document AEs
- Document concomitant therapies
- Document any change to physiotherapy since the previous study visit
- Assess if subject has clinically relevant improvement, and if so, initiate oral corticosteroid taper
- Individual CSMs
- CDASI

#### 8.5.4.4 Week 41

The following procedures will be conducted at 40 weeks  $\pm$  3 days after the first SC infusion of IMP:

- Body weight
- IMP assignment
- Vital signs
- Safety assessments
- Collection of urine sample for hCG pregnancy test, if applicable
- Collection of blood samples to assess the following:
  - Muscle enzymes
  - Coagulation
- Subject SC Infusion Diary review
- Document AEs
- Document concomitant therapies
- Document any change to physiotherapy since the previous study visit
- Assess if subject has clinically relevant improvement, and if so, initiate oral corticosteroid taper
- Individual CSMs
- CDASI
- 5-D Itch Score
- Timed Up and Go
- EQ-5D-5L, WPAI-GH, TSQM-9

### 8.5.4.5 Week 45

The following procedures will be conducted at 44 weeks  $\pm$  3 days after the first SC infusion of IMP:

- Body weight
- IMP assignment
- Vital signs
- Safety assessments
- Collection of urine sample for hCG pregnancy test, if applicable
- Collection of blood samples to assess the following:
  - Hematology
  - Muscle enzymes
  - Other biochemistry
  - Coagulation
- Subject SC Infusion Diary review
- Document AEs
- Document concomitant therapies
- Document any change to physiotherapy since the previous study visit
- Assess if subject has clinically relevant improvement, and if so, initiate oral corticosteroid taper
- Individual CSMs
- CDASI

### 8.5.4.6 Week 49

The following procedures will be conducted at 48 weeks  $\pm$  3 days after the first SC infusion of IMP:

- Body weight
- IMP assignment
- Vital signs

- Safety assessments
- Collection of urine sample for hCG pregnancy test, if applicable
- Collection of blood samples for exploratory biomarkers (serum analysis)
- Collection of blood samples to assess the following:
  - Muscle enzymes
  - Coagulation
  - Serum IgG
- Subject SC Infusion Diary review
- Document AEs
- Document concomitant therapies
- Document any change to physiotherapy since the previous study visit
- Assess if subject has clinically relevant improvement, and if so, initiate oral corticosteroid taper
- Individual CSMs
- CDASI

#### 8.5.4.7 Week 53

Eligibility for continuation of treatment in Study Period 3 is based on a TIS of  $\geq 20$  points at Week 49 and is to be confirmed at the Week 53 Visit. If the subject is not eligible to continue treatment with IgPro20, study participation will end with the Week 56 Safety Follow-up Telephone Call (see [Section 8.5.4.8](#)). If a subject is withdrawn from the study before the Week 53 Visit, the investigator should make every effort to perform the assessments scheduled for the Week 53 Visit:

- General physical examination
- 12-lead ECG
- Body weight
- Waist circumference
- IMP assignment, if subject is eligible to continue treatment with IgPro20 in Study Period 3

- Vital signs
- Safety assessments
- Collection of urine sample for hCG pregnancy test, if applicable
- Collection of blood samples for virology retention and exploratory biomarkers (RNA and serum analyses)
- Collection of blood samples to assess the following:
  - Hematology
  - HbA1c
  - Muscle enzymes
  - Other biochemistry
  - Coagulation
  - Serum IgG
  - ANA, MSA, and MAA
- Subject SC Infusion Diary review
- Document AEs
- Document concomitant therapies
- Document any change to physiotherapy since the previous study visit
- DOW (only applicable to subjects who discontinue IMP treatment before Week 25)
- Individual CSMs
- CDASI
- 5-D Itch Score
- Timed Up and Go
- EQ-5D-5L, WPAI-GH, TSQM-9

- Document reason for withdrawal, if applicable
- Assess the subject's eligibility for treatment continuation in Study Period 3, if applicable

#### **8.5.4.8 Week 56 (Safety Follow-up Telephone Call)**

If a subject is not eligible to continue treatment with IgPro20 in Study Period 3, a telephone call to assess AEs and concomitant therapies will occur 4 weeks after last IMP infusion, after which no further study-related procedures will be performed. In this case, the Safety Follow-up Telephone Call constitutes the EOP2 Visit. The Safety Follow-up Telephone Call will not be performed for subjects who discontinue IMP treatment but remain in the study for at least 1 subsequent study visit 4 weeks after IMP discontinuation, or for subjects who continue treatment with IgPro20 in Study Period 3.

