**Notes for the Schedule of Assessments for Study Period 1 and Study Period 2:**

- After up to 2 months of Screening, the duration for an individual subject is expected to be 24 weeks in Study Period 1 and 28 weeks in Study Period 2. The maximum study duration in the open-label Study Period 3 may be approximately 7 years; however, subject participation will end if the drug becomes available or if there is no longer benefit from the study drug. For subjects not eligible to participate in Study Period 3, study duration will be up to 56 weeks (including the Follow-up Telephone Call).
- Study Period 1 starts at the Baseline Visit and continues to Week 25. Baseline assessments must be completed before the Week 1 assessments. Study Period 2 starts after the assessments at the Week 25 Visit and continues through the Week 53 Visit for subjects who are eligible and continue long-term treatment with IgPro20 in Study Period 3, or through the Week 56 Telephone Visit (EOP2) for subjects whose study participation ends with Study Period 2.
- For subjects who discontinue IMP early during participation in Study Period 1 or Study Period 2, all Week 53 assessments will be performed at the study visit where IMP treatment is discontinued instead of the assessments scheduled for that particular study visit.
- Confirmation per Treating and Evaluating Physicians that no clinically relevant improvement has occurred since Screening and that the subject is still eligible for the study.
- This study assessment will not be performed at any study visit after discontinuation of IMP treatment.
- Additional IMP will be assigned at UNS Visit if the subject's weight has increased (> 2 kg), which will require a dose volume increase (see [Appendix 15](#)).
- Only if subject is eligible for continuation of treatment in Study Period 3.
- Vital sign assessments include supine systolic and diastolic blood pressure, pulse rate, respiratory rate, and body temperature.
- Safety assessments: Monitoring for corticosteroid treatment, monitoring for TEEs (including Wells' Criteria score for DVT and/or Wells' Criteria score for PE), monitoring for hemolysis at Week 2 and Week 5 only.
- Urine hCG pregnancy test is to be completed for all premenopausal females capable of becoming pregnant. This includes women on oral, injectable, or mechanical contraception and women whose partners have been vasectomized or have received or are utilizing mechanical contraceptive devices.

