- AA. Six individual CSMs will be assessed during the study for TIS calculation: (1) Physician Global Disease Activity, (2) Patient Global Activity Assessment, (3) Manual Muscle Testing of 8 muscle groups (MMT-8), (4) HAQ, (5) Muscle Enzyme, and (6) Extramuscular Global Assessment.
- BB. TSQM-9 is not performed at Baseline.
- CC. The Week 56 Safety Follow-up Telephone Call will not be performed for subjects who discontinue IMP treatment before Week 53 but remain in the study for at least 1 subsequent study visit 4 weeks after IMP discontinuation or subjects who are eligible to continue treatment in Study Period 3.

**Table 3** Schedule of Assessments for Open-label Study Period 3

	Subsequent Years (4-week cycles)					
	Study Week	Every 4 weeks	Every 24 weeks	End of Year	UNS	EOP3
Time Window	±7d	±7d	±7d	NA	±7d	
Assessments						
Urine hCG pregnancy test B		X	X	X	X	
Physical examination			X			X
Vital signs C		X	X	X	X	
Body weight	X	X	X	X	X	
Virology retention sample						X
Hematology and biochemistry D, E			X	X	X	
Efficacy assessments (4 individual CSMs) F		X	X	X	X	
CDASI		X	X	X	X	
EQ-5D-5L		X	X	X	X	
IMP assignment G	X	X	X H			
IMP SC weekly infusions	X	X	X H			
Subject SC Infusion Diary Review	X	X	X	X	X	
AEs	◀				▶	
Concomitant therapies	◀				▶	

AE = adverse event; BUN = blood urea nitrogen; CDASI = Cutaneous Dermatomyositis Disease Area and Severity Index; CSM = core set measure; d = day

EQ-5D-5L = EuroQoL 5-Dimension Questionnaire; EOP3 = End of Study Period 3; GGT = gamma-glutamyl transferase; HAQ = Health Assessment Questionnaire; hCG = human chorionic gonadotropin; IMP = investigational medicinal product; M = month; MMT-8 = Manual Muscle Testing of 8 muscle groups; NA = not applicable; SC = subcutaneous; UNS = unscheduled visit; W = week.

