At Week 53, eligibility for continuation of open-label IgPro20 treatment in Study Period 3 will be confirmed based on the TIS conducted in Week 49 (see [Section 4.1.3](#) for details). If subjects do not continue treatment after Week 53, an EOP2 Safety Follow-up Telephone Call will be conducted to assess the subject's safety status at Week 56 (or 4 weeks after the final infusion). If the subject continues treatment in Study Period 3, the telephone call will not be performed.

See [Section 3.7](#) for the definition of study end.

Figure 1

Study Design

Abbreviations: DM = dermatomyositis; DOW = Definition of Worsening; EOP = End of Study Period; TIS = Total Improvement Score.

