**Table 16****Study Periods and Reference Visits**

Study Period	Weeks	Start of Study Period	Reference Visit of Period	End of Period A
1	Week 1 to Week 25	Start date and time of the first IMP infusion	Baseline (before infusion of IMP)	Week 25 (before infusion of IMP)
2	Week 25 to Week 53/Week 56	Start date and time of the first IMP infusion at Week 25	Baseline (before infusion of IMP)	Week 53 (before infusion of IMP) / Week 56 (for subjects not entering SP3)
			Week 25 (before infusion of IMP)	
3	Week 53 to EOP3	Start date and time of the first IMP infusion at Week 53	Week 53 (before infusion of IMP)	EOP3

IMP = investigational medicinal product; EOP3 = End of Study Period 3; SP3 = Study Period 3.

A The end of the period is the listed study visit or the last study visit before/at withdrawal.

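### The protocol gives two conflicting triggers for the Week 56 safety call, so an eligible subject who stops at Week 53 could be left without it

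*Protocol*

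**What the plan says.** Eligibility for Study Period 3 rests on one criterion, a TIS of at least 20 at Week 49 (Protocol Section 4.1.3 and Glossary). Entry is then permitted, not required.

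Some passages make the safety call depend on **eligibility**:
- Section 8.5.4: "Subjects not eligible for participation in Study Period 3 must complete the Week 56 Safety Follow-up Telephone Call".
- Section 8.5.4.7: for a subject who is not eligible, participation ends with the Week 56 call.
- Section 8.5.4.8, first sentence: "If a subject is not eligible to continue treatment with IgPro20 in Study Period 3, a telephone call to assess AEs and concomitant therapies" takes place 4 weeks after the last infusion.
- Schedule of Assessments for Periods 1 and 2, note CC: among those for whom the call is not made, "or subjects who are eligible to continue treatment in Study Period 3".
- The 56-week duration statements in the Synopsis, the first schedule note and Section 3.4 are also limited to subjects who are not eligible.

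Others make it depend on **what the subject actually does**:
- Section 3.1: "If subjects do not continue treatment after Week 53, an EOP2 Safety Follow-up Telephone Call will be conducted"; and then "If the subject continues treatment in Study Period 3, the telephone call will not be performed".
- Table 16, end of Study Period 2: "Week 53 (before infusion of IMP) / Week 56 (for subjects not entering SP3").
- The schedule's note on periods runs Period 2 through the Week 56 telephone visit "for subjects whose study participation ends with Study Period 2".
- Section 8.5.4.8, last sentence, exempts certain subjects who stopped IMP early, "or for subjects who continue treatment with IgPro20 in Study Period 3".
- SAP Table 8 footnote b repeats the Section 3.1 rule.

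**The concern.** The two rules agree for a subject who is not eligible (call) and for one who is eligible and enters Period 3 (no call). They part for the subject who is eligible and chooses not to go on. Note CC excludes that subject from the call in terms, while Section 3.1 requires it. No passage says which prevails.

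Sites schedule visits from the Schedule of Assessments and Section 8.5, which is where most of the eligibility wording sits. Under Section 9.4 the observation period for adverse events closes at the last completed visit. Without the call that is Week 53, only days after the last dose. What is at stake is the planned post-treatment contact for these subjects, in a study that treats thromboembolic events as events of special interest and includes Period 2 data in its comparison of them (SAP Section 11.3).

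**Working it through.** The point turns on wording. The only arithmetic is the length of the window at risk.

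**Step 1. Apply each rule to each kind of Period 2 completer.**

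| Subject at Week 53 | Eligibility wording | Continuation wording |
|---|---|---|
| Not eligible | Call | Call |
| Eligible, enters Period 3 | No call | No call |
| Eligible, does not enter | No call (note CC) | Call |

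Only the third row conflicts. It can occur because entry is optional.

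**Step 2. Reproduce the plan's own timing.** Section 3.1 treats Week 56 as equivalent to 4 weeks after the final infusion. Take the nominal day of Week w as (w − 1) × 7 + 1. The last dosing week of Period 2 is Week 52 (SAP Section 8.2.24), and its infusions must be finished before the Week 53 visit (Protocol Section 5.1.3).
- Week 52 dosing: days 358 to 364.
- Week 53 visit: (53 − 1) × 7 + 1 = day 365.
- Week 56 call: (56 − 1) × 7 + 1 = day 386.
- Last infusion to call: 386 − 364 = 22 days to 386 − 358 = 28 days. Four weeks is reproduced when counted from the start of Week 52 dosing.

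**Step 3. Length of the window at risk.**
- Last infusion to Week 53 visit: 365 − 364 = 1 day to 365 − 358 = 7 days. Adverse events in this interval are documented at Week 53 under either rule.
- Week 53 visit to call: 386 − 365 = 21 days. This is the interval without planned contact if note CC is followed. Under the continuation wording it is 0 days.

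These are nominal days; visits carry a window of ±3 days.

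**Step 4. Scale, by assumption only.** The documents give neither a decline rate nor an expected number of Period 2 completers. Suppose 100 complete and 10% to 20% are eligible but do not enter:
- Time lost: 10 × 3 = 30 to 20 × 3 = 60 subject-weeks.
- Period 2 time: 100 × 28 = 2,800 subject-weeks.
- Share: 30 / 2,800 = 1.1% to 60 / 2,800 = 2.1%.

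**The case against.** The best answer is that the intent is clear. Section 3.1, Table 16, the schedule's note on periods and the SAP all bring a decliner into the call, and Section 8.5.4.8 itself ends by exempting those who continue, not those who are eligible. Section 4.3.2.1 also asks for every effort to complete the 4-week call for subjects withdrawn in Periods 1 and 2. This stands as evidence of intent. It does not cancel note CC, which is an express waiver in the table that sites work from. Nor is it clear that someone who completes Period 2 and declines an optional extension has been withdrawn.

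A reader might go further and infer that eligible decliners get no call and that their adverse events after the last infusion are not collected. The documents do not support that:
- Several passages require the call for them.
- Events up to Week 53 are recorded, and unresolved ones are followed after participation ends (Sections 9.5 and 9.6.1).
- Later SAEs with a possible causal link to IMP must be reported if the investigator learns of them (Section 9.4), although SAEs reported after participation ends are not entered in the eCRF (Section 9.6.3).

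A reader might also infer that Period 2 adverse event rates are biased by unequal follow-up. That argument is weak. SAP Section 11.2 annualizes rates over observational time, and subjects who continue end Period 2 at Week 53 by design, so unequal follow-up would remain after any correction. That decliners tend to have tolerability problems is plausible but not documented.

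**Conclusion.** The point holds as an internal contradiction with a small consequence for safety data. For an eligible subject who does not enter Study Period 3, one set of passages waives the Week 56 call and another requires it. If a site follows note CC, adverse events in a nominal 21 days are not systematically solicited. Non-serious events are the most exposed, because later reporting reaches only SAEs with a possible link to IMP that come to the investigator's attention.

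The number of such subjects is unknown. The 1.1% to 2.1% of Period 2 time rests wholly on the assumed 100 completers and 10% to 20% decline rate. The primary endpoint, alpha, power and sample size are unaffected. This is a minor point, worth correcting because correction is cheap.

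**What to change.** Make actual entry the single trigger, as Section 3.1, Table 16 and SAP Table 8 already have it:
- In Sections 8.5.4 and 8.5.4.7 and the first sentence of 8.5.4.8, replace not eligible with not entering Study Period 3.
- In note CC, replace eligible to continue with entering Study Period 3, and leave its other exemption (early IMP discontinuation with a later visit) as it is.
- In the 56-week duration statements (Synopsis, first note to the Periods 1 and 2 schedule, Section 3.4), refer to subjects who do not enter Study Period 3. Otherwise the same mismatch survives there.

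The SAP needs no change. The cost is a few words in seven places and a telephone call, already a study procedure, for each eligible subject who declines. No dose or treatment rule is touched.
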